### **2.4.4. Safety Set**

The Safety Set consists of all randomized participants who receive any study injection. The Safety Set will be used for all analyses of safety except for the solicited ARs.

Participants will be included in the vaccination group corresponding to the study injections that they actually received.

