## **2.5. Statistical Analysis**

### **2.5.1. General Considerations**

The Schedule of Assessments is provided in [Appendix F](#).

**Continuous variables** will be summarized using the following descriptive summary statistics: the number of participants (n), mean, standard deviation (SD), median, minimum (min), and maximum (max). For the summary statistics of all numerical variables, unless otherwise specified, the display precision will follow programming standards. Please see [Appendix A](#) for variable display standards.

**Categorical variables** will be summarized using counts and percentages. When count data are presented, the percentage will be suppressed when the count is zero to draw attention to the non-zero counts. A row denoted “Missing” will be included in count tabulations where specified on the shells to account for dropouts and missing values. The denominator for all percentages will be the number of participants in that vaccination group within the analysis set of interest, unless otherwise specified.

**Baseline value** is defined as the most recent non-missing measurement (scheduled or unscheduled) collected before the first injection, unless otherwise specified. For immunogenicity tests, the baseline is defined as the most recent non-missing result/measurement (scheduled or unscheduled) collected before or on the date of the first injection (Day 1). If there are multiple valid results on the same date, the largest value will be considered in the immunogenicity baseline derivation.

**Study day relative to the Day 1 injection** will be calculated as below:

- a) Study day prior to the Day 1 injection will be calculated as: date of assessment/event – date of the Day 1 injection (resulting in negative study day).
- b) Study day on or after the date of the Day 1 injection will be calculated as: date of assessment/event – date of the Day 1 injection + 1.

For GMT and GMC calculation, antibody values reported as below the LLOQ will be replaced by  $0.5 \times \text{LLOQ}$  and antibody values greater than the ULOQ will be converted to the ULOQ.

**Unscheduled visits:** Unscheduled visit measurements will be included in analysis as follows:

- In the derivation of baseline measurements.
- In scheduled visit windows per specified visit windowing rules.
- In individual participant data listings as appropriate.

**Visit windowing rules:** The analysis visit windows for protocol-defined visits are provided in [Appendix B](#), Table 5.

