#### **2.5.3.2. Adverse Events**

An AE is defined as any untoward medical occurrence in a clinical trial participant administered a medicinal drug product and which does not necessarily have a causal relationship with this treatment. AEs will also be evaluated by the investigator for the coexistence of MAAE which is defined as an AE that leads to an unscheduled visit to an HCP.

A TEAE is defined as any event occurring during the study not before exposure to study vaccine. Worsening of a pre-existing condition after vaccination will be reported as a new AE.

An unsolicited TEAE is any AE reported by the participant that is not specified as a solicited AR in the protocol or is specified as a solicited AR but starts outside the protocol-defined period for reporting solicited ARs (i.e., 7 days after study vaccine administration). For analysis and reporting purpose, unsolicited TEAEs will include the following:

- TEAEs that are reported by participants and recorded on the AE eCRF
- Solicited ARs that meet SAE criteria and are recorded on the Reactogenicity eCRF

Unsolicited AEs will be collected for up to 28 days after injection; SAEs, MAAEs, AESIs, and AEs leading to study discontinuation will be collected throughout the study. Unsolicited TEAEs will be summarized up to 28 days after injection unless otherwise specified. Additionally, SAEs, MAAEs, AESIs and AEs leading to study discontinuation will be summarized throughout the study (up to Day 181/EoS). Refer to Safety Estimand 4b in [Appendix I, Table 10](#).

All summary tables (except for the overall summary of TEAEs) for unsolicited TEAEs will be presented by SOC and PT (or by PT). SOC will be displayed in internationally agreed order. PTs will be displayed in descending order of frequency in the mRNA-1345 (█  $\mu$ g) + Afluria Quadrivalent group and then alphabetically within SOC. When summarizing the number and percentage of participants with an event, participants with multiple occurrences of the same AE or a continuing AE will be counted once.

For the by severity summaries, the toxicity grade of a solicited AR meeting SAE criteria after injection will be mapped to a severity level of Mild/Grade 1, Moderate/Grade 2 or Severe/ $\geq$  Grade 3 and the maximum severity level in the case of multiple events will be presented.

Percentages will be based upon the number of participants in the Safety Set within each vaccination group.

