## **3.2. Study Endpoints**

### **3.2.1. Primary Endpoints**

#### **3.2.1.1. Primary Safety Endpoints**

The primary safety objective will be evaluated by the following safety endpoints:

- Numbers and percentages of participants with solicited local and systemic ARs over the 7 days after each injection.
- Numbers and percentages of participant with unsolicited AEs through 28 days after each injection.
- Numbers and percentages of participants with MAAEs, SAEs, AESIs, and AEs leading to withdrawal from Day 1 (baseline) to EoS.

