### 3.4. Analysis Populations

Please see [Section 2.4](#) for details, except of the following:

- Supportive PP Set will not be applicable in Part B.
- PP Set consists of all participants in the FAS who receive the assigned Day 1 study injections according to protocol regardless of Day 29 injection, comply with immunogenicity blood sampling to have a baseline and at least one Day 29 post-injection assessment within the visit window of study day [22, 43], and have no major protocol deviations that impact the immune response.
- Additionally, 2 subsets of the Solicited Safety Set are defined for Day 1 injection and Day 29 injection. Day 1 (Day 29) Solicited Safety Set consists of all participants in the Solicited Safety Set who have received the study injection on Day 1 (Day 29) and have contributed any solicited AR data (eDiary) from the time of study injection on Day 1 (Day 29) through the following 6 days.

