#### **3.5.2. Background Characteristics**

##### **3.5.2.1. Participant Disposition**

Please see [Section 2.5.2.1](#) for details. Differences for Part B are listed as the following:

The number and percentage of participants in each of the following disposition categories will be summarized by vaccination group based on the Randomization Set:

- Received Day 1 injection
- Received Day 29 injection
- Completed the study
- Prematurely discontinued the study and the reason for discontinuation

A participant, who has completed the last scheduled procedure on Day 211 (i.e., 7 months after administration of the study injections on Day 1), is considered to have completed the study.

The number and percentage of participants in each of the following disposition categories will be displayed by vaccination group based on the Safety Set:

- Received Day 1 injection
- Received Day 29 injection

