### **3.5.3.2. Adverse Events**

Please see [Section 2.5.3.2](#) for details. Differences for Part B are listed as the following:

Unsolicited TEAEs will be summarized up to 28 days post each injection (Day 1 and Day 29). Additionally, SAEs, MAAEs, AESIs and AEs leading to study discontinuation will be

summarized considering all events up 7 days after each injection (Day 1 and Day 29), and throughout the study (up to Day 211/EoS).

Refer to Safety Estimand 9b in [Appendix I](#), Table 12.

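### Part B: if unsolicited adverse events are tabulated per injection, the post-Day 29 percentages keep participants who never received that injection in the denominator and run low by the share who missed it

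*SAP*

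**What the plan says.** - **Denominator.** SAP 2.5.3.2 (Adverse Events, Part A) sets it: "Percentages will be based upon the number of participants in the Safety Set within each vaccination group". The general rule in SAP 2.5.1 agrees: "The denominator for all percentages will be the number of participants in that vaccination group within the analysis set of interest, unless otherwise specified".
- **Safety Set.** SAP 2.4.4: "The Safety Set consists of all randomized participants who receive any study injection". The Part B exceptions in SAP 3.4 do not alter this set.
- **Part B windows.** One of the primary safety endpoints in SAP 3.2.1.1 is "Numbers and percentages of participant with unsolicited AEs through 28 days after each injection". SAP 3.5.3.2 refers back to 2.5.3.2 and lists its differences, beginning with "Unsolicited TEAEs will be summarized up to 28 days post each injection (Day 1 and Day 29". It adds a 7-day window after each injection for SAEs, MAAEs, AESIs and AEs leading to study discontinuation. Only the windows change.
- **Solicited reactions.** SAP 3.4 treats these by injection: "Additionally, 2 subsets of the Solicited Safety Set are defined for Day 1 injection and Day 29 injection". Each subset requires receipt of the injection concerned.
- **Missed Day 29 doses.** SAP 3.4 admits to the PP Set participants "who receive the assigned Day 1 study injections according to protocol regardless of Day 29 injection". SAP 3.5.2.1 tabulates "Received Day 29 injection" on the Safety Set. SAP 3.5.3.2.2 adds a Part B table of events leading to discontinuation from study vaccine, and Day 29 is the only injection left to discontinue after Day 1.

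**The concern.** Under SAP 3.5.1, the clock for the most recent injection restarts only when the Day 29 injection is given. A participant who misses that injection has no post-Day 29 window and cannot contribute an event to it. The stated rule still counts that participant in the denominator. The SAP avoids this for solicited reactions and has no equivalent for unsolicited events.

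What is at stake is the accuracy of a descriptive rate within a primary safety endpoint. It matters most for Group 4, for whom Day 29 is the only dose of mRNA-1273.214; Groups 5 and 6 receive placebo that day. A percentage read as the event rate after that dose would be somewhat too low.

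**Working it through.** **Inputs from the documents**
- Group size: 560 per group (SAP 3.3.3).
- Safety Set: any injection (SAP 2.4.4).
- Post-Day 29 window: starts at the Day 29 injection (SAP 3.5.1).

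**Inputs assumed, because the documents give none**
- Share of the Safety Set missing Day 29, written m: 2% to 10%.
- True post-Day 29 rate among recipients: 10% or 15%, for illustration.

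**Step 1. The plan's own figure.** SAP 3.3.3 states about a 94% chance of seeing at least one participant with an event at a true rate of 0.5%. Check: 1 − 0.995^560 = 0.9396. It reproduces. If the same statement were applied to the Day 29 injection with 10% missed (n = 504), it would be 1 − 0.995^504 = 0.920.

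**Step 2. The printed percentage.** Non-recipients add nothing to the numerator, so

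printed rate = true rate × (number given Day 29 ÷ number in Safety Set) = true rate × (1 − m).

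| m (assumed) | true 10% prints as | true 15% prints as |
|---|---|---|
| 0% | 10.0% | 15.0% |
| 2% | 9.8% | 14.7% |
| 5% | 9.5% | 14.25% |
| 10% | 9.0% | 13.5% |

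The relative understatement equals m.

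**Step 3. The same in counts.** Take 50 participants with an event after Day 29 in a group of 560.
- As written: 50/560 = 8.93%.
- Recipients only, 2% missed (n = 549): 50/549 = 9.11%.
- Recipients only, 10% missed (n = 504): 50/504 = 9.92%.

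**Step 4. Between arms.** With equal true rates of 15% but non-receipt of 3% in one arm and 8% in another (both assumed), the tables print 15% × 0.97 = 14.55% and 15% × 0.92 = 13.80%, a gap of 0.75 points. For scale, the standard error of a difference at 15% with 560 per arm is √(2 × 0.15 × 0.85 ÷ 560) = 0.0213, a 95% half-width of about 4.2 points. With equal non-receipt and equal true rates there is no gap.

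**Step 5. Are the summaries per injection?** The wording points two ways.
- *Per injection:* SAP 3.2.1.1, SAP 3.5.3.2 and Safety Estimand 9b all say *each injection*. Where the SAP pools the two windows, for medications and procedures (3.5.2.4 and 3.5.2.5), it says *any injection*.
- *Combined:* SAP 3.5.3.1 says solicited reactions are presented *separately* after each injection; 3.5.3.2 does not use that word. Protocol 3.8.1.2 adds a Day 29 summary for solicited reactions only.

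The contrast of *each* with *any* favours per-injection tables but does not settle it.

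**The case against.** The strongest reply is that SAP 3.5.3.2 may intend one table covering both 28-day windows. Everyone dosed on Day 1 would then be properly in the denominator and nothing would be wrong. This cannot be ruled out, so the point is conditional. If a combined table is meant, the section still needs a sentence saying so.

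A second reply is that the denominator matches Safety Estimand 9b, whose target population is adults who receive the IP administration, with no requirement tied to a particular injection. That is fair as far as the population goes. But the same estimand describes the proportion with an event within 28 days after each injection, and a person not given an injection has no such period.

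A third is that the loss is recoverable. The overview tables print counts, and Day 29 receipt is tabulated by group on the Safety Set, so a reader can recompute those percentages. This limits the harm; it is not a reason to print the wrong figure.

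Three stronger readings are tempting, and the documents do not support them:
- *That the arm comparison in the primary safety objective is biased.* That objective concerns coadministration, which occurs only on Day 1. Post-Day 1 and throughout-study percentages are unaffected, and nothing shows that Day 29 receipt differs by arm.
- *That the post-Day 29 rates are understated whatever happens.* The bias is zero if nobody misses the dose.
- *That different denominators for solicited and unsolicited tables are themselves a defect.* Those tables use different analysis sets by design, including in single-visit Part A.

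**Conclusion.** The point holds conditionally. To the extent that SAP 3.5.3.2 produces per-injection summaries, its inherited denominator makes post-Day 29 percentages too low by a relative amount equal to the Day 29 non-receipt rate. This covers the 28-day unsolicited events and the 7-day SAEs, MAAEs, AESIs and AEs leading to study discontinuation.

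The absolute size rests on assumed inputs: at a true 15%, the shortfall is 0.3 points with 2% missed and 1.5 points with 10% missed. The effect is small and the summaries are descriptive; no noninferiority test or success criterion changes. It is worth correcting because the SAP foresees missed Day 29 doses and already has the matching device for solicited reactions.

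**What to change.** 1. In SAP 3.4, define a Day 29 Safety Set: Safety Set participants who received the Day 29 injection, by group actually received, parallel to the Day 29 Solicited Safety Set.
2. In SAP 3.5.3.2, state that post-Day 1 and post-Day 29 summaries are presented separately, and that every window starting at the Day 29 injection, including the 7-day ones, uses the Day 29 Safety Set as denominator.
3. Keep the full Safety Set for post-Day 1, combined any-injection and throughout-study summaries.

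The cost is about two sentences and one population flag, built on a count that SAP 3.5.2.1 already requires. No data collection changes. Post-Day 29 percentages will be slightly higher if any doses are missed.

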#### 2.5.3.2.1. Overview of TEAEs

Overall summary of unsolicited TEAEs up to 7 days post-injection, between 8 to 28 days post-injection, and up to 28 days post-injection will be provided, for the number and percentage of participants, along with the number of events, by vaccination group who experience at least one of the categories:

- Any unsolicited TEAEs
- Any serious TEAEs
- Any fatal TEAEs
- Any unsolicited medically-attended TEAEs
- Any unsolicited TEAEs leading to study discontinuation
- Any unsolicited severe TEAEs
- Any unsolicited non-serious TEAEs (no SAE)

- Any unsolicited non-serious severe TEAEs (no SAE)
- Any unsolicited non-serious TEAEs (regardless of SAE)
- Any unsolicited non-serious severe TEAEs (regardless of SAE)
- Any unsolicited AESI

Note: Severe TEAEs include both unsolicited severe TEAEs and  $\geq$  Grade 3 solicited ARs that meet SAE criteria after injection.

Summary tables will also be provided to include number and percentage of participants with unsolicited treatment-related TEAEs up to 28 days post-injection. Additionally, the overall summary for the categories of SAEs, MAAEs, AESIs, and AEs leading to study discontinuation will be provided for these TEAEs throughout the study. Separate listings containing individual participant AE data up to EoS for unsolicited TEAEs, serious TEAEs, unsolicited medically-attended TEAEs, unsolicited AESIs, unsolicited TEAEs leading to study discontinuation, severe TEAEs, fatal unsolicited TEAEs, and unsolicited AESIs will be provided.

#### **2.5.3.2.2. TEAEs by System Organ Class and Preferred Term**

The following summary tables of unsolicited TEAEs up to 28 days after injection will be provided by SOC and PT using frequency counts and percentages (i.e., number and percentage of participants with an event):

- All unsolicited TEAEs
- All unsolicited TEAEs that are treatment-related
- All serious TEAEs
- All serious TEAEs that are treatment-related
- All unsolicited non-serious TEAEs
- All unsolicited non-serious severe TEAEs
- All unsolicited medically-attended TEAEs
- All unsolicited medically-attended TEAEs that are treatment-related
- All unsolicited TEAEs leading to study discontinuation
- All unsolicited severe TEAEs
- All unsolicited severe TEAEs that are treatment-related
- All unsolicited treatment emergent AESI

Note: Severe TEAEs include both unsolicited severe TEAEs and  $\geq$  Grade 3 solicited ARs that meet SAE criteria after injection.

Summary tables will also be provided for number and percentage of participants with unsolicited TEAEs up to 7 days post-injection, between 8 to 28 days post-injection, and up to 28 days post-injection, and be presented by SOC and PT.

Additionally, summary tables of SAEs, treatment-related SAEs, MAAEs, treatment-related MAAEs, TEAEs leading to study discontinuation, AESIs, and TEAEs leading to death will be also provided by SOC and PT considering all events reported throughout the study. Number of events and number of participants will also be summarized by SOC and PT for participants with AESI up to 7 days post-injection, up to 28 days post-injection, and throughout the study.

#### **2.5.3.2.3. TEAEs by Preferred Term**

A summary table for all unsolicited TEAEs up to 28 days after injection will be provided by PT in descending order of frequency in the mRNA-1345 (█  $\mu$ g) + Afluria Quadrivalent group.

#### **2.5.3.2.4. TEAEs by Severity**

The following summary tables of TEAEs up to 28 days after injection will be provided by the severity, SOC and PT using frequency counts and percentages:

- All unsolicited TEAEs
- All unsolicited TEAEs that are treatment-related

Summary tables of unsolicited TEAEs up to 28 days after injection with occurrence in  $\geq 1\%$  of participants in any vaccination group based on preferred term will be also provided by severity, SOC and PT.

#### **2.5.3.2.5. TEAEs by System Organ Class, High Level Group Term, and Preferred Term**

Certain TEAEs, as indicated in [Appendix K](#), will also be summarized by SOC, HLGT, and PT for each vaccination group and presented by three time periods: up to 7 days post-injection, up to 28 days post-injection, and up to EoS after post-injection.

#### **2.5.3.2.6. Independent Cardiac Event Adjudication Committee**

An independent CEAC of medically qualified personnel, including cardiologists, will review suspected cases of myocarditis and pericarditis to determine if they meet CDC criteria of “probable” or “confirmed” events, and to assess severity (see more details in Section 3.7.6 of the protocol) and provide the assessment to the Sponsor. The CEAC members will be blinded to study

treatment. Details regarding the CEAC composition, responsibilities, procedures, and frequency of data review can be found in the CEAC charter.

A summary table will be provided based on the data adjudicated by the CEAC, as the primary analysis of cardiac events.

#### **2.5.3.2.7. Subgroup Analysis of TEAEs**

The overview of TEAEs, TEAEs by SOC/PT, TEAEs by Severity, unsolicited treatment-related TEAEs by SOC/PT and serious TEAEs by SOC/PT may be provided for the following subgroup:

- Age group (50 to 59 years, 60 to 74 years,  $\geq$  75 years)
- Age group (50 to 59 years,  $\geq$  60 years)
- Sex (male, female)
- Race (White, Black, Asian, other [including American Indian or Alaska Native, Native Hawaiian or other Pacific Islander and other races])

These summaries may be provided for additional subgroups of selected baseline characteristics.

#### **2.5.3.3. Vital Sign Measurements**

Vital signs will only be collected at Screening and on the day of injection (Day 1), once before and at least 30 minutes after injection. Vital signs will be collected at other study visits only in conjunction with a symptom-directed physical examination.

Vital sign measurements, including systolic and diastolic blood pressures, pulse, respiratory rate and body temperature will be presented in a data listing. The values meeting the toxicity grading criteria will be flagged in the data listing.

Observed pre-injection and post-injection values and change from pre-injection to post-injection at Day 1 will be summarized by vaccination group. Shift from pre-injection to post-injection in the toxicity grades will also be summarized by vaccination group.

The abnormalities meeting the toxicity grading criteria (Grade 2 or higher) in any vital sign measurement will be listed separately. If a participant has a vital sign result with Grade 2 or higher abnormality after injection visit, then all results of that specific vital sign for that participant will be presented in the listing.

## 2.5.4. Immunogenicity Analysis

The analyses of immunogenicity will be using the PP Set, by vaccination group. The supportive analyses of immunogenicity especially for primary immune response will be conducted using the FAS based on [Appendix I](#). If the number of participants in the FAS and PP Set differ (defined as the difference divided by the total number of participants in the PP Set) by more than 10%, additional supportive analyses of non-primary immunogenicity may be conducted using the FAS.

The GMT, GMC, and GM level will be calculated using the following formula:

$$10^{\left\{ \frac{1}{n} \sum_{i=1}^n \log_{10}(y_{it}) \right\}}$$

where  $y_{1t}, y_{2t}, \dots, y_{nt}$  are  $n$  observed immunogenicity titers or levels for participants  $i=1, 2, \dots, n$  at time point  $t$ .

The GMFR measures the changes in immunogenicity titers or levels from baseline within participants. The GMFR will be calculated using the following formula:

$$10^{\left\{ \frac{1}{n} \sum_{i=1}^n \log_{10}\left(\frac{y_{it}}{y_{i0}}\right) \right\}} = 10^{\left\{ \frac{1}{n} \sum_{i=1}^n [\log_{10}(y_{it}) - \log_{10}(y_{i0})] \right\}}$$

where  $y_{1t}, y_{2t}, \dots, y_{nt}$  are observed immunogenicity titers or levels for participants  $i$ 's at time point  $t$ . and  $y_{10}, y_{20}, \dots, y_{n0}$  are immunogenicity titers or levels for participants  $i$ 's at time point 0 (baseline).

